4.6 Calculated Variables

Baseline is defined as the last assessment value before or on the date of the first IMP administration in this trial unless specified otherwise.

Confidential

Date/time of first study treatment in the listings refers to first IMP administration in the base trial.

Study days for visit date, assessment date, date of progression and date of death are calculated versus the start of IMP administration in the base trial.

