10.1 Anti-tumor Activity

Anti-tumor activity measured by tumor shrinkage (based on sum of the diameter(s) of all target lesions from the CT or MRI scan evaluations) will be listed. Details of target lesions (method, lesion location and specification, description, longest and shortest diameter), non-target lesions (method, lesion location and specification, description, lesion status and specification) and new lesions (method, lesion site and specification and description) will be included. Response assessments including the target lesion overall response, non-target lesion overall response, new lesion status, overall response and date of disease progression will be listed in a separate listing. Disease response or progression should be evaluated according to the current published RECIST (Response Evaluation Criteria In Solid Tumors) version 1.1 (Eisenhauer et al., 2009¹). Baseline will be defined as the last assessment before the first IMP administration in the base trial. Local tumor assessment information available from the base trials will be included in these listings.

 Confidential

Results obtained from an independent, central imaging review will be included when available.

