10.2 CA 125 (Ovarian cancer only)

CA 125 values over time including the change from baseline from the initial trial will be listed.

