11.1 Extent of Exposure

The listing of extent of exposure will include the treatment administration date and start and end times, the planned dose and planned total dose, dose adjusted (Yes/No) and reason (including AE and details for Other), actual dose administered, the actual volume infused, administration interrupted (Yes/No) including times and reason, planned dose administered (Yes/No) and reason if not and treatment label identifier. Number of infusions in this trial and in total since start in the base trial will be added as well as the cumulative dose since start of the treatment in the base trial.

Exposure information from the base trials will be included in the listing.

Ocular AE mitigation plan administrations in relation to infusions will be included in this listing.

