11.7 Vital Signs and ECG

ECG measurements will be listed including the evaluation (Normal/Abnormal, not clinically significant/Abnormal, clinically significant).

All vital signs results will be listed including a flag for clinically notable values for each of the following parameters:

Clinically notable elevated values

- Systolic BP: ≥ 180 mmHg and an increase ≥ 20 mmHg from baseline
- Diastolic BP: ≥ 105 mmHg and an increase ≥ 15 mmHg from baseline.
- Weight: Increase from baseline of 10%
- Heart rate: ≥ 120 bpm with increase from baseline of ≥ 15 bpm
- Temperature: > 38 °C

Clinically notable below normal values

- Systolic BP: ≤ 90 mmHg and a decrease ≥ 20 mmHg from baseline
- Diastolic BP: ≤ 50 mmHg and a decrease ≥ 15 mmHg from baseline
- Weight: decrease from baseline of $\geq 10\%$
- Heart rate: ≤ 50 bpm with decrease from baseline of ≥ 15 bpm
- Temperature: < 35 °C

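### The weight, blood-pressure and heart-rate flags in SAP 11.7 start from entry to this trial, so they do not count change that built up on the drug in the base trial

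*SAP*

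**What the plan says.** The general rule is in SAP 4.6: "Baseline is defined as the last assessment value before or on the date of the first IMP administration in this trial unless specified otherwise".

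Two efficacy sections depart from it. For tumor assessments, SAP 10.1 states: "Baseline will be defined as the last assessment before the first IMP administration in the base trial". For the ovarian marker, SAP 10.2 states: "CA 125 values over time including the change from baseline from the initial trial will be listed".

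Several other quantities also run from the base trial:
- study days (SAP 4.6);
- AE start and end days (SAP 11.2);
- the total number of infusions and the "cumulative dose since start of the treatment in the base trial" (SAP 11.1);
- the start of the treatment period (SAP 4.1.1, which adds that periods are not used in the analysis).

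SAP 11.7 states: "All vital signs results will be listed including a flag for clinically notable values for each of the following parameters". Most of its criteria compare with baseline, for example "Weight: decrease from baseline of" 10% or more, and a heart rate of at least 120 "bpm with increase from baseline of" 15 bpm or more. It does not say which baseline applies, so the default in 4.6 governs.

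SAP 4 names three kinds of data to be brought in from the base trials: medical history, local tumor assessments and exposure. Vital signs are not among them.

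**The concern.** Every patient reaches this trial after treatment with tisotumab vedotin in GEN701 or GEN702. The entry value of weight, blood pressure or heart rate is therefore an on-drug value. A flag defined as change from that value cannot count what happened earlier in the same course of treatment.

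The primary objective is long-term safety (SAP 3.1.1). A slow change spread over both trials is the kind of pattern a rollover trial is well placed to show. It can stay below the threshold when the course is split in two. The analysis consists of listings, so these flags are the only derived signal planned for vital signs. The SAP gives no reason why they start at entry when the tumor, CA 125, AE-day and exposure data do not.

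**Working it through.** The plan gives no figure to reproduce here. The check applies the SAP 11.7 rules under each baseline.

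**Which flags are affected.** SAP 11.7 lists ten criteria, five high and five low. The two for temperature are absolute limits ("Temperature: > 38 °C" and the matching low limit of 35 °C). The other 10 − 2 = 8 use change from baseline. Weight has no absolute limit. Blood pressure and heart rate need both an absolute value and a change.

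**Weight loss.** Let b be the fraction of pre-drug weight lost before entry. The flag is silent while current weight stays above 0.90 of entry weight, that is, above 0.90 × (1 − b) of pre-drug weight. Unflagged total loss can therefore approach, but not reach, 1 − 0.90 × (1 − b). With a pre-treatment baseline the flag fires at 10% total loss, so the further in-trial loss needed is 1 − 0.90/(1 − b), or none once b is 10% or more. The values of b are assumptions.

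| b (assumed) | Unflagged total loss can approach | In-trial loss that triggers the flag: SAP as written | In-trial loss that triggers the flag: pre-treatment baseline |
|---|---|---|---|
| 0% | 1 − 0.90 × 1.00 = 10.0% | 10% | 10% |
| 5% | 1 − 0.90 × 0.95 = 14.5% | 10% | 5.3% |
| 8% | 1 − 0.90 × 0.92 = 17.2% | 10% | 2.2% |
| 10% | 1 − 0.90 × 0.90 = 19.0% | 10% | 0% |

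**Single-patient illustrations (invented values).**

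| Measure | Before drug | At entry | Now | Change from pre-drug | Change from entry |
|---|---|---|---|---|---|
| Weight (kg) | 80 | 74 | 67 | −13/80 = −16.25%, flag | −7/74 = −9.46%, no flag |
| Systolic BP (mmHg) | 135 | 165 | 182 | +47, flag | +17, no flag |
| Heart rate (bpm) | 80 | 110 | 122 | +42, flag | +12, no flag |
| Weight (kg), after gain in the base trial | 80 | 86 | 77 | −3/80 = −3.75%, no flag | −9/86 = −10.47%, flag |

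The last row shows the opposite effect: the entry baseline produces a flag that the pre-treatment baseline would not.

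**Can the reader recover the pre-drug value?** For weight, roughly. Base-trial exposure goes into the exposure listing, which holds planned dose and planned total dose. If these are in mg/kg and mg, their ratio gives the dosing weight. That weight would be rounded, and also capped at a BMI of 30 if the base trials used the rule in Protocol 9.2. For blood pressure and heart rate, nothing imported supplies a pre-drug value.

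**The case against.** The best defense is that an entry baseline is legitimate. It isolates change during this trial, the period in which these vital signs are collected, and it needs no outside data. That stands, and the fix keeps it.

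A second defense is that little is concealed. About 25 patients are expected, every vital-sign value is listed by patient and visit, and the flag feeds no table, test or decision rule. The primary endpoint is adverse events (Protocol 7). All AEs are recorded and graded, so weight loss or hypotension that an investigator judges to be an AE is captured whatever the flag does. This also stands, and it limits the importance of the point.

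Three stronger readings are tempting, and the documents do not support them:
- **All safety flags are reset at entry.** They are not. The ocular, overdose and medication-error, and special-interest flags in SAP 11.2 use no baseline value. Neither do the laboratory flag in SAP 11.6 or the temperature criteria. AE days and cumulative dose run from the base trial.
- **The split favors the drug throughout.** The entry baseline can add flags as well as remove them, as the weight-gain example shows. Running AE days and exposure from the base trial does not fit a pattern of discarding earlier harm.
- **Harm in the base trial is lost.** AEs before consent go into the base-trial eCRF (Protocol 11.2), and aggregated safety data are analyzed across trials (Protocol 11.8). Whether the base trials flagged vital-sign change cannot be known from these documents.

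**Conclusion.** The point holds for the eight change-based criteria in SAP 11.7 and no further. These flags are measured from an on-drug value at entry, while tumor response, CA 125, study days, AE days and cumulative exposure run from the base trial. The SAP does not explain the difference. For weight, unflagged total loss can approach 14.5% if 5% was lost before entry and 19% if 10% was lost. How often this would occur cannot be estimated.

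The conclusion rests on reading the 4.6 default into 11.7, which the absence of any override supports, and on taking the list of imported data in SAP 4 at face value. That list may be incomplete, since SAP 10.2 also needs a base-trial CA 125 value, but nothing in 11.7 calls for base-trial vital signs. No error rate, power or sample size is affected. This is a worthwhile, inexpensive improvement to a listing that serves the primary objective.

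**What to change.** - **SAP 4:** add base-trial pre-dose weight, blood pressure and heart rate to the data brought in from the base trials.
- **SAP 4.6:** define a pre-treatment baseline for these measures, namely the last value before the first IMP administration in the base trial, and keep the entry baseline beside it.
- **SAP 11.7 and Listing 16.02.03.13:** derive the eight change-based flags against both baselines, with a separate letter for each, and state which letter refers to which. Where no base-trial value exists, use the entry baseline alone.

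The cost is SAP wording, one more transfer from base-trial databases that already supply medical history, tumor and exposure data, and one extra flag column. A few more values will be flagged. The change assumes that the base trials recorded pre-dose vital signs, which these documents do not confirm.

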4.7 Partial/Missing Dates

Partial or missing dates will not be imputed as the data will only be listed. All information available will be presented.

4.8 Methods to Be Used For Handling Missing Data

All available data will be included in data listings and tabulations.

No imputation of missing data is planned.

4.9 Changes to Protocol

Summary tables might be created as needed.

5. Trial Patients

5.1 Disposition of Patients

Date of signing the ICF (including additional ICFs), version and date of ICF, base trial, last trial drug intake date in the base trial, screening failure and the reason, the primary reason for discontinuation of the trial including the reason for 'other' and the reason for withdrawal by patient, date of progression and date of death will be included.

A listing of all visits will be created including the reason for unscheduled visits and a flag if target/non-target assessment is done.

5.2 Protocol Deviations

The protocol deviations will be listed including a flag for major deviations.

Protocol violations will be defined in the protocol deviations plan.

5.3 Inclusion and Exclusion Criteria

Listing of all inclusion and exclusion criteria not met together with the protocol version will be provided.

6. Demographic and Baseline Disease Characteristics

In the listing of demographic characteristics, the variables to be listed are:

- Gender (Male/Female)
- Age (Years), date of birth
- Race (White, Black or African American, Native Hawaiian or other Pacific Islander, Asian, American Indian or Alaska native, Other + details)
- Ethnicity (Hispanic or Latino, Not Hispanic or Latino)
- ECOG performance score (0-5). Note: at entry only patients with an ECOG performance score of 0 and 1 are allowed.

 Confidential

- Childbearing potential (Yes/No and reason)
- Cancer type (Ovary, Cervix, Endometrium, Bladder, Prostate, Head and neck, Esophagus, Lung)

7. Medical History

Medical conditions will be coded using the Medical Dictionary for Regulatory Activities (MedDRA).

The medical conditions will be listed including term, system organ class and preferred term, start and end date, ongoing flag and started more than 1 year ago flag.

The medical history from the base trial will be reported.

8. Subsequent Cancer Therapies

All subsequent cancer therapies, except for surgeries, will be listed including the anatomical therapeutic chemical (ATC) code level 2 and active ingredient (WHO-DD dictionary). Surgeries will be coded using the Medical Dictionary for Regulatory Activities (MedDRA) and presented including system organ class and preferred term.

9. Prior and Concomitant Medications

Prior and Concomitant medications will be classified according to World Health Organization Drug Dictionary.

Medications will be flagged according to the following 3 distinct categories:

[figure not shown]
- Prior when they start and end before the first day of trial treatment.
- Prior and ongoing when they start before the first day of trial treatment and stop or continue after the first day of trial treatment.
- Medications will be reported as concomitant when they start on or after first day of trial treatment.

A listing of all medications recorded on the (prior and) concomitant medications CRF page will provide details including indication, dose, route, frequency, start and stop dates, prior/concomitant flag, active ingredient and ATC class.

10. Efficacy Evaluation

10.1 Anti-tumor Activity

Anti-tumor activity measured by tumor shrinkage (based on sum of the diameter(s) of all target lesions from the CT or MRI scan evaluations) will be listed. Details of target lesions (method, lesion location and specification, description, longest and shortest diameter), non-target lesions (method, lesion location and specification, description, lesion status and specification) and new lesions (method, lesion site and specification and description) will be included. Response assessments including the target lesion overall response, non-target lesion overall response, new lesion status, overall response and date of disease progression will be listed in a separate listing. Disease response or progression should be evaluated according to the current published RECIST (Response Evaluation Criteria In Solid Tumors) version 1.1 (Eisenhauer et al., 2009¹). Baseline will be defined as the last assessment before the first IMP administration in the base trial. Local tumor assessment information available from the base trials will be included in these listings.

 Confidential

Results obtained from an independent, central imaging review will be included when available.

10.2 CA 125 (Ovarian cancer only)

CA 125 values over time including the change from baseline from the initial trial will be listed.

10.3 ECOG Performance Status

ECOG performance status results will be listed.

11. Safety Evaluation

11.1 Extent of Exposure

The listing of extent of exposure will include the treatment administration date and start and end times, the planned dose and planned total dose, dose adjusted (Yes/No) and reason (including AE and details for Other), actual dose administered, the actual volume infused, administration interrupted (Yes/No) including times and reason, planned dose administered (Yes/No) and reason if not and treatment label identifier. Number of infusions in this trial and in total since start in the base trial will be added as well as the cumulative dose since start of the treatment in the base trial.

Exposure information from the base trials will be included in the listing.

Ocular AE mitigation plan administrations in relation to infusions will be included in this listing.

11.2 Adverse Events

Adverse events (AEs) will be coded using the Medical Dictionary for Regulatory Activities (MedDRA) and will be graded according to the National Cancer Institute Common Terminology Criteria for AEs (NCI CTCAE criteria version 4.03, 2010).

[figure not shown]
Adverse events will be listed including the reported term (verbatim), system organ class and preferred term, start and end date/time, start and end day relative to the date of the start date of treatment in the base trial, outcome, toxicity grade, seriousness, relationship to the trial treatment and infusion, action taken and if supporting clinically significant laboratory results.

A flag will be added to mark if the AE occurs before the first IMP administration in this trial, or after the last IMP administration in this trial. In addition, flags will be added to mark ocular adverse events, overdose and medication errors and adverse events of special interest (Bleeding-related events, neuropathy and ocular events).

11.3 Deaths and Serious Adverse Events

The same listing as above will be repeated for:

- Serious AEs
- Fatal AEs
- NCI CTCAE Grade 3/4 AEs
- AEs leading to discontinuation of the IMP
- Non-serious grade 2 or higher ocular events.

Confidential

All deaths will be listed separately including the source CRF page (fatal AEs, reason for withdrawal on End of trial form) and the death date.

11.4 Neuropathy and Skin Assessment

Neuropathy and skin assessment data will be listed.

11.5 Ophthalmological Evaluations

Visual acuity, Schirmer's tear test, SLIT lamp, Intraocular pressure, Fundoscopy and overall evaluation results will be listed.

11.6 Clinical Laboratory Data

All laboratory results will be listed including the test name, result, unit and normal ranges. Supporting clinically significant laboratory results will be flagged.

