8.2 Schedule of Activities

Table 1: Trial Flow Chart - 1Q3W Treatment Scheme

Procedure	Screening (up to 21 days before Day 1)	Treatment Period Cycle 1 – X (21-day cycle \pm 7 days) Day 1	End-of-Trial Visit (30 days after last dose + 1 week)	Comments
Informed consent	X			
Eligibility criteria	X			
Demography	X			
Height	X			
Weight	X	X		To be taken at screening and at start of each treatment cycle
Pregnancy test	X	X		To be taken at screening and at start of each treatment cycle for women of childbearing potential
Vital signs	X	X		Blood pressure pulse, heart rate and temperature taken at screening and before and after treatment
ECG	X	X		To be taken at screening and before each treatment
ECOG performance status	X			
Neuropathy assessment	X			
Skin assessment	X			
Ophthalmology evaluation	X	X	X	To be performed according to the schedule in the base protocol. Patients experiencing ocular symptoms must be referred to an ophthalmologist for prompt review (preferably within 72 hours and no later than within 1 week).
Laboratory sampling	X	X	X	Local laboratories will be used. Screening laboratory samples do not need to be repeated if performed at the base trial. Details on laboratory samples are provided in Section 10.3.4.

Procedure	Screening (up to 21 days before Day 1)	Treatment Period Cycle 1 – X (21-day cycle \pm 7 days) Day 1	End-of-Trial Visit (30 days after last dose + 1 week)	Comments
Trial drug administration		X		Treatment administration schedule to follow the treatment schedule in the base protocol.
Preventive eye therapy		X		Preventive eye therapy to be administered in relation to infusions as detailed in Section 9.5.4.
Response assessment (CT-scan, PSA, CA 125)	X	X	X	Last CT-scan of base trial to be used at screening if less than 4 weeks old, otherwise a new CT-scan needs to be obtained. Then, to be performed every 6 weeks (at the end of every second cycle) during Treatment Period, and response to be confirmed 4 weeks later. Response assessments will be recorded in the eCRF. PSA will be performed for CRPC patients. CA 125 will be performed for patients with ovarian cancer.
Radionuclide bone scan		X		For patients with CRPC, assessment of bone metastases by radionuclide bone scan every 12 weeks is recommended, but frequency should be based on local standards. If there is suspicion of progression, another bone scan will be performed twelve weeks later.
AE/SAE review	X	X	X	
Concomitant medication	X	X	X	

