8.5.1 Inclusion Criteria

Patients **MUST** satisfy all of the following entry criteria before they will be allowed to participate in the trial:

1. Patients must have either:
 - a) completed the base trial and have shown a clinical benefit of SD or better and have never met any withdrawal criteria as defined in the tisotumab vedotin base protocol, or
 - b) not completed treatment as defined in the base protocol for reasons that are not considered critical and unmanageable for the safety of the patient (as evaluated by the investigator and/or the sponsor) and the patient clearly showed response of PR or better.

2. Patients must not have experienced radiographic disease progression or clinical signs of symptoms of instability requiring urgent intervention.
3. Patients must not have received any other anti-cancer treatment (including surgery, radiation or systemic chemotherapy) since the base trial.
4. Acceptable renal function defined as: Glomerular filtration rate (Cockcroft-Gault) > 45 mL/min.
5. Acceptable liver function defined as:
 - a) Alanine aminotransferase and aspartate aminotransferase ≤ 3 times the upper limit of normal (ULN); if liver tumor/metastases are present, then $\leq 5 \times$ ULN is allowed,
 - b) Bilirubin $\leq 1.5 \times$ ULN, except in patients diagnosed with Gilbert's syndrome, direct bilirubin $\leq 2 \times$ ULN.
6. Acceptable hematological status (hematologic support is allowed if administered at least one week before scheduled Cycle 1 Day 1) defined as:
 - a) Hemoglobin ≥ 5.6 mmol/L (~ 9 g/dL). An absolute value > 8 g/dL is allowed if stable (> 4 weeks) during the base trial.
 - b) Absolute neutrophil count $\geq 1500/\mu\text{L}$ ($1.5 \times 10^9/\text{L}$).
 - c) Platelet count $\geq 75 \times 10^9/\text{L}$.
7. Eastern Cooperative Oncology Group (ECOG) performance status of 0 or 1.
8. A negative serum pregnancy test (if female and aged between 18-55 years old).
9. Patients, both females and males, of reproductive potential must agree to use adequate contraception during and for six months after the last infusion of tisotumab vedotin.

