10.3.3 Electrocardiograms

Single 12-lead ECG will be obtained as outlined in the Schedule of Activities ([Table 1](#)) using a local ECG machine that automatically calculates the heart rate and measures PR, QRS, QT, and QTc intervals. ECG results will not be recorded in the eCRF except for clinically significant results that must be reported as an AE.

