10.3.4 Clinical Safety Laboratory Assessments

Laboratory tests should be collected as outlined in the Schedule of Activities ([Table 1](#)) and assessed in accordance with local standards. Screening laboratory samples do not need to be repeated if these were performed as part of the base trial within 21 days before Cycle 1 Day 1 of the current trial. Laboratory results will not be recorded in the eCRF except for clinically significant results that must be reported as an AE. If a laboratory result is deemed to be an AE, this should be reported in the eCRF including the laboratory value and the relevant reference range. Retesting is required only if clinical symptoms appear.

A blood sample for pregnancy test will be drawn at the Screening Visit and at the start of each treatment cycle from all women of childbearing potential.

The following safety laboratory tests should be collected:

Hematology

Erythrocytes, hemoglobin, hematocrit, leukocytes, neutrophils, lymphocytes, monocytes, eosinophils, basophils, neutrophils (absolute), lymphocytes (absolute), monocytes (absolute), eosinophils (absolute), basophils (absolute) and reticulocytes.

Coagulation

Prothrombin time (INR), aPTT and prothrombin time (sec).

Biochemistry

Sodium, potassium, calcium, magnesium, albumin, glucose, creatinine, creatinine clearance (Cockcroft-Gault), uric acid, blood urea nitrogen, aspartate aminotransferase, alanine aminotransferase, alkaline phosphatase, bilirubin (total), lactate dehydrogenase, creatinine kinase and C-reactive protein.

Serology (only at screening)

Hepatitis B surface antigen, anti-hepatitis B core antigen, anti-hepatitis C virus, cytomegalovirus (CMV) IgG, CMV IgM, human papilloma virus screening, CMV DNA, hepatitis C virus RNA (qualitative).

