11.8 Pregnancy Test

All pregnancy test data will be listed.

12. References

Confidential

13. List of Tables/Graphs/Listings

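### Does the SAP promise laboratory, ECG and pregnancy-test listings that the protocol's eCRF rule cannot fill?

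*SAP*

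**What the plan says.** Three short SAP sections bear on this. On laboratory data, SAP 11.6 promises that "All laboratory results will be listed including the test name, result, unit and normal ranges", and it adds a flag for clinically significant supporting results. On ECGs, SAP 11.7 says "ECG measurements will be listed including the evaluation (Normal/Abnormal, not clinically significant/Abnormal, clinically significant"). On pregnancy tests, SAP 11.8 says "All pregnancy test data will be listed". These become Listings 16.02.03.11, 16.02.03.12 and 16.02.03.14 in SAP 13.3.

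The protocol describes narrower capture for two of the three. Section 10.3.4: "Laboratory results will not be recorded in the eCRF except for clinically significant results that must be reported as an AE". Section 10.3.3: "ECG results will not be recorded in the eCRF except for clinically significant results that must be reported as an AE". The pregnancy test is also described in 10.3.4, in a later paragraph: "A blood sample for pregnancy test will be drawn at the Screening Visit and at the start of each treatment cycle", for women of childbearing potential.

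Two general provisions in SAP 4 also apply. All data collected in this trial are to be listed, and the reason an assessment was not done is to be shown where that applies. SAP 4.9, which declares departures from the protocol, mentions only optional summary tables.

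**The concern.** Listings are the only planned output of this trial, so it matters that they contain what the plan says. If the eCRF follows the protocol, a normal haemoglobin or a normal ECG never reaches the database. A reader who takes Listing 16.02.03.11 to be complete could then read a missing row as a normal result, when it might equally be an abnormal result judged not significant, or a test that was not done.

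Pregnancy tests look like the sharpest case, because there the negative result is the informative one. Inclusion criterion 8 requires "A negative serum pregnancy test (if female and aged between 18-55 years old"), and the test is repeated at each cycle. If the 10.3.4 restriction covered these tests, negative results would not be entered and the listing could not show that the scheduled tests had been done. If instead the eCRF holds everything, the protocol misdescribes what is collected. On either reading, one document seems to need correcting.

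**Working it through.** There is no figure to reproduce: the trial has no formal sample size, alpha or power. The check is a comparison of texts, one data type at a time, followed by a count.

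**Laboratory.** The SAP lists all results and flags the clinically significant ones. The protocol admits only clinically significant results that must be reported as AEs. If only those are in the database, the flag marks every row and tells the reader nothing. The flag makes better sense if other results are listed too. The two texts do not match.

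**ECG.** SAP 11.7 does not use the word *all* for ECGs; it uses it in the next sentence, for vital signs. It does print three evaluation classes. Under Protocol 10.3.3, two of the three (normal, and abnormal but not clinically significant) would have no eCRF data. The classes may be a printed code list, as with the ECOG scale in SAP 6, which runs from 0 to 5 although only 0 and 1 may enter. The mismatch holds in substance, less firmly than for laboratory data.

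**Pregnancy test.** The restriction in 10.3.4 is on laboratory results. The pregnancy test has its own paragraph and is absent from that section's list of safety laboratory tests. In Table 1 it has its own row, and the pointer to 10.3.4 sits in the separate laboratory-sampling row. The SAP makes the same split, with 11.6 for laboratory data and 11.8 for pregnancy tests. No sentence limits entry of pregnancy-test results, so a conflict can only be inferred. Table 1 does not help the inference. It says of response assessments that "Response assessments will be recorded in the eCRF" and says nothing similar for pregnancy tests, but it is equally silent on height, weight and AEs, all of which the protocol elsewhere requires in the eCRF (10.1.3 and 11.2).

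**Count.** Safety listings run from 16.02.03.01 to 16.02.03.14, which is 14. Those with a mismatch are .11 and .12, so 2 of 14. With 9 general and 4 efficacy listings, the total is 9 + 4 + 14 = 27, so 2 of 27 overall. Planned tables: none (SAP 13.1). Endpoints affected: none.

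**What is lost.** The primary endpoint is adverse events. Protocol 10.3.4 requires a laboratory AE to be entered with its value and reference range, and 10.3.3 requires a clinically significant ECG finding to be reported as an AE. SAP 11.2 lists every AE and marks whether clinically significant laboratory results support it. The findings that matter for safety therefore reach a listing whichever text is accurate.

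**The case for a change.** The strongest case for a change is that the laboratory conflict is direct and survived a revision. SAP version 2.0 was updated for protocol versions 3 to 5 and dropped the PSA and bone-scan listings because no prostate cancer patients were enrolled. Listings were trimmed to fit the data, yet this mismatch stayed, and SAP 4.9 does not declare it. Reading *all* as everything collected does not explain why a flag is needed. An absent screening row is also ambiguous: Protocol 10.3.4 lets base-trial samples stand in for screening samples, while SAP 4 brings over only medical history, tumor assessments and exposure. The remedy would be a footnote.

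Most of that stands as description. The wording mismatch is real for laboratory and ECG data, and the SAP's reason-not-done provision helps only if the eCRF has such a field for these tests. What does not follow is a gain from changing the plan. A footnote would repeat a capture rule that Protocol 10.3.3 and 10.3.4 already state. Correcting the protocol instead is more than a wording matter, since Protocol 15.2 requires any change to go through an amendment. Which of the two is needed cannot be decided from these documents.

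The worry that nothing could show pregnancy tests were done is also too strong. Entry criteria not met are listed (SAP 5.3), protocol deviations are listed (SAP 5.2), and monitors check protocol compliance and verify eCRF entries against source documents (Protocol 13).

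**Conclusion.** The concern holds in part and calls for no change. SAP 11.6 and 11.7 describe wider laboratory and ECG data than Protocol 10.3.4 and 10.3.3 allow into the eCRF. This is loose wording in 2 of 14 safety listings. Under SAP 4 the programmer lists what was collected, so the listings come out the same whether or not the sentences are aligned. No planned result, endpoint or conclusion changes.

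For pregnancy tests no conflict is established. Whether the 10.3.4 restriction was meant to reach them is at most a question for the sponsor.

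The conclusion rests on two assumptions: that clinically significant findings are entered as AEs, as the protocol requires, and that the listings stay listings. SAP 4 and 4.9 allow optional summary tables. If one gave percentages of laboratory or ECG abnormalities, the capture rule would determine its denominator and would have to be stated with it. None is planned. The eCRF and the data management plan, to which Protocol 14.1 leaves the origin and transfer of data, were not available, so it remains open which text describes the actual capture.
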